5.2. INVESTIGATION PLAN*

List Interventions	Baseline assessment	3 rd month visit	9 th month visit	Other monthly visits
Training plans	Prior to baseline assessment	N/A	N/A	N/A
Information delivery session & Informed Consent	V	N/A	N/A	N/A
Inclusion / Exclusion criteria	Prior to the initial visit	N/A	N/A	N/A
Anthropometry assessment	✓	√	✓	√
Dietary intake exam	✓	✓	✓	✓
Sun exposure exam	✓	✓	✓	✓
Pill count	N/A	✓	✓	✓
Adherence assessment with Problem & strategies session	√	√	√	√
Adverse Event Assessment	✓	✓	✓	√
Blood test	✓	✓	✓	Х

Training and certification plans

(Prior to baseline assessment, Earlwood medical centre, approx. 50 min)

We will have the General Practitioners (GPs) who believed to meet GCP requirement with appropriate qualification and skill to conduct the trial and will have the 'study therapists' to assist them. 'Study therapists' must attend the compulsory training session for this research only prior to the commencement of the study, which will facilitate their understanding of the trial and their roles.

Information delivery session

(Baseline assessment only; Earlwood medical centre; approx. 30min)

- The importance of following study guidelines for adherence to daily study intervention;
- Instructions about taking supplements including dosage, storage and what to do in the event of a missed dose; notification there will be a pill count at every study visit;
- Instructions about how to apply the food list into real life and how to record daily dietary
 intake by using the smartphone application 'East Diet Diary' or by a paper-based food diary
 and what to do if miss to record; notification there will be a dietary diary examination at
 monthly study visit;

- Instructions about clothing, timing, weather condition for sun exposure and how to record daily sun exposure time on the paper-based diary and what to do if miss to record; notification there will be a sun exposure diary exam at monthly study visit;
- The importance of notifying the clinic if experiencing problems possibly related to study products such as side effects, upset symptoms, lost pills or food lists or diary books.

Anthropometry assessment

(Each visit; Earlwood Medical Centre; approx. 10min)

- Weight (kg) is measured by a digital scale (Tanita UM-051).
- BMI is calculated out based on equation: BMI=weight (kg)/height² (m²).
- Waist and hip ratio is measured by a measuring tape and calculated.

Data collection: dietary data exam / sun exposure exam/ pill count

(Each visit; Earlwood Medical Centre; approx. 20min)

- Pill count- Participants will return the unused tablets and bottle at each follow-up visit. Unused tablets will be counted and recorded on the appropriate CRF (case report form).
- A 24-hour food recall and a Food Frequency Questionnaire (FFQ) will be used at baseline to collect nutritional information of energy, protein, fat, carbohydrate and vitamin D. A 3-day food diary (2 workdays and 1 weekend day per week, hence four copies per month) is used for each follow-up visit. Diary can be completed through either paper-based diary or the smartphone application 'EasyDietDiary'. If participants failed to complete the diary, a 24 hr recall and a FFQ will be used to collect the missing information. An Accredited Practicing Dietitian (APD) will be appointed to design the dietary guideline and provide training to study therapists who conduct the nutritional information collection; data will be later processed through 'FOODWORK 8' database.
- Sun exposure time will be evaluated by the Sun exposure questionnaire (adapted from 45 and up Questionnaire) at baseline. Research staff will check the Sun exposure diary at each follow-up visit. Participants will be asked to do extra diary entries to compensate if they missed recording the information. We use the scoring from weekly sun exposure recall questionnaire (Hanwell et al. 2010) to assess the sun exposure status.

Adherence session

(During the whole trial)

- Maintain interest in the study through mailings and phone calls;
- Send letters to participants prior to the monthly follow up assessment, and ring on the previous day to remind the next day assessment;
- Provide assistance if participants have questions of the diet menu, or participants who experience food intolerance and allergy symptoms;
- Provide participants with information about the current status of the study, and plans for the next phase, as well as to acknowledge their support

Problem and strategy session

(Each visit; Earlwood Medical Centre; approx. 5min)

 Participants will be asked about any problems they have regarding taking their study supplements or use of the diaries. There will be a brief discussion of reasons for missed doses and simple strategies for enhancing adherence, eg, linking supplement taking to meals or other daily activities; schedule an outdoor time in noon; update the diet intake daily through phone applications.

Adverse event assessment

(Each visit, Earlwood medical centre, approx. 5min)

Adverse events will be collected after the participant has provided consent and enrolled

in the study. There is the possibility that in the dietary intervention group, some subjects may report food intolerance and/or allergy symptoms to seafood or dairy products. We will record the incidences; APD will provide dietetics consultation and appropriate suggestion to minimize the risks. If the adverse effects continue, participants will be excluded from the trial, allergy test and related medical treatment will be provided if necessary.

Blood test

(Baseline assessment, 3^{rd} month and 9^{th} month only; Earlwood medical centre; approx. 10 min)

 A government accredited Pathology Collection point or the Registered Nurses at Earlwood Medical Centre will collect the blood samples and forward the sample to the NATA accredited pathology laboratory to conduct the blood test for the Diabetes biomarker and serum 25OH D.

5.3. STUDY PROCEDURE RISKS*

Adverse events will be collected after the participant has provided consent and enrolled in the study. In the current trial, the dosage of vitamin D (500 IU) provided through supplementary, dietary or sun exposure is considered to be safe and it is unlikely to cause adverse effects. However, if participants report with any adverse effects, they will be provided with medical treatment if necessary and excluded from the trial.

Other than that, there is the possibility that in the dietary intervention group, some subjects may report with food intolerance and allergy symptoms to seafood or dairy products. Research staff will record the incidences. Participants will be asked to attend a dietitian review for appropriate suggestion to minimize the risks. If the adverse effects are continued, participants will be excluded from the trial, related test or medical treatment will be provided if necessary.

5.4. RECRUITMENT AND SCREENING*

Trial information will be provided through website, flyer and local advertising. The trial will also be introduced to GPs and allied health professionals for cross-referral recruitment. Participants who express an interest through email, phone calls and personal attendance at clinics will be recruited. These include self-referred participants and participants who are referred by a GP or health professional. Diabetic patients' lists (name only) in both clinic centres will be used to contact for an EOI (expression of interest) as well. Responses to any inquiries about participation in the research study are to be answered by a phone that is manned during business hours and answered by voicemail at all other times. A research assistant will respond to each inquiry immediately, using a screening instrument to identify eligible participants and provide the following instructions.

5.5. INFORMED CONSENT PROCESS*

Once patients identify an interest in the trial, they will be directed to read the website information or information package and eventually sign the consent form and prepare to attend for the baseline assessment.

5.6. ENROLMENT PROCEDURE*

The research staff will enrol the participants following the confirmation of the consent form and eligibility.

5.7. RANDOMISATION PROCEDURE

Allocation: Sequence generation

Participants will be randomly assigned to one of four different groups with an equal ratio referring to the permuted block randomisation. The software randomisation package MINUM will be used for sequence generation. The block sizes will not be disclosed, to ensure concealment.

Allocation concealment mechanism

Allocation concealment will be ensured, as the centre will not release the randomisation code until

the participants have been recruited into the trial. The randomisation will be conducted by an independent investigator (not the research student) and send the sequence to study therapists who are only responsible for implementing the randomisation.

Implementation

All participants who give consent for participation, and who fulfil the inclusion criteria, will be randomized. An independent investigator (not the research student) will send the randomisation instruction to the study therapist who is not involved in recruitment or outcome assessment. Follow the randomisation instrument, eligible study therapist prepares closed envelopes with printed randomisation numbers and are available in both recruitment centres. For every randomisation number, the corresponding code for the intervention group will be found inside the envelope. Only the study therapist will open the envelope and will find the treatment to be conducted for this participant. The therapist then gives the information about treatment that allocated to the patient. The randomisation list will be stored in the two centres for the whole time period of study.

6.SAFETY*

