3. STUDY DESIGN*

3.1. DESIGN*

The D4D trial is designed as a multi-centre, single-blind, randomized, parallel group, superiority study, to determine the role of vitamin D from the oral supplement, sun exposure and dietary invention in controlling and reducing DM risks. Randomisation will be performed as block randomisation with an equal ratio allocation through MINUM, a computer program that randomises and stratifys participants equally into the different arms of the study.

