7. BLINIDING AND UNBLINDING

The study therapist blind to treatment allocation will conduct the baseline assessment/monthly assessment for the anthropometry, dietary and sun exposure data collection. The pathology technician who is blind to treatment allocation will conduct the blood test. Due to the nature of the intervention, neither participants nor assessors will be blinded to the intervention but will be informed not to disclose the allocation status or status of the participant at the follow-up assessments. An employee outside the research team will input data into the computer in separate datasheets so that the research team can analyse data without having access to information about the allocation.

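### Allocation concealment is asserted but not assured, because the list sits at the recruiting centres, and the protocol contradicts itself on who is blinded

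*Protocol*

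**What the plan says.** **Concealment (protocol section 5.7).** The section states that concealment will be ensured. An independent investigator runs the randomisation and is to "send the sequence to study therapists who are only responsible for implementing the randomisation". Then "eligible study therapist prepares closed envelopes with printed randomisation numbers and are available in both recruitment centres". Only the study therapist opens an envelope, and the therapist tells the participant the arm. Finally, "The randomisation list will be stored in the two centres for the whole time period of study". Section 3.4 identifies the two centres as the recruitment sites.

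The safeguards offered are closed envelopes, undisclosed block sizes, a code that is not released until the participant has been recruited, and a "study therapist who is not involved in recruitment or outcome assessment". Section 5.6 gives enrolment to research staff.

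**Blinding.** The synopsis and section 3.1 describe a "multi-centre, single-blind, randomized, parallel group, superiority study" without naming the blinded party. Section 7 states: "The study therapist blind to treatment allocation will conduct the baseline assessment/monthly assessment". It then calls the pathology technician blind, and the next sentence says that "neither participants nor assessors will be blinded to the intervention". It closes by arranging data entry so that the research team can analyse without knowing the allocation. Section 5.2 has study therapists collect the nutritional information.

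**The concern.** Concealment depends on nobody involved in recruitment being able to learn the next allocation before a participant is entered. A list kept at the recruiting sites for the whole study, with no stated custodian or access limit, leaves that to chance. The four arms (supplement, diet, sun exposure, wait list) differ visibly and may appeal to different patients. If the next arm were known, the timing or offer of enrolment could be influenced. Blind laboratory work would not prevent this: it protects how HbA1c is measured, not who enters which arm. Adjustment in the analysis would correct only for factors that were measured.

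The blinding statements matter separately. A reader of the protocol or the trial report cannot tell whether the clinic-collected measures were taken blind, and the label single-blind suggests a protection that section 7 withdraws.

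**Working it through.** The plan gives no figure on this point, so the check sets the passages side by side. One illustration of predictability follows.

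**1. Who can know the sequence?**

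| Step | Stated in | Who or where |
|---|---|---|
| Generates and sends sequence | 5.7 | Independent investigator |
| Receives sequence | 5.7 | Study therapists |
| Prepares envelopes | 5.7 | Study therapist |
| Holds envelopes | 5.7 | Both recruitment centres |
| Holds list | 5.7 | Both centres, whole study |
| Enrols | 5.6 | Research staff |
| Opens envelope, announces arm | 5.7 | Study therapist |

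Each safeguard can be tested against one question: does it stop someone at the centre from reading the list?
- Closed envelopes protect their contents, not the list.
- Undisclosed block sizes hinder guessing from past allocations. They are irrelevant to someone who can see the list.
- Release of the code only after recruitment is a rule about disclosure. The text makes the centre the party that withholds the code. If that means a clinic, the recruiting site holds what it must not see.
- A therapist outside recruitment limits what that person can do, but does not restrict access for others on site.

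**2. How much does access to the list change?** Assume one sequence, four equal arms and permuted blocks. The block size is not given, so 4, 8 and 12 are assumed.
- Chance: 1/4 = 25% correct.
- Block of 4, past allocations and block size known: the best guess succeeds with probability 1/4, 1/3, 1/2 and 1 at the four positions. The mean is (0.250 + 0.333 + 0.500 + 1.000)/4 = 2.083/4 = 52%. One allocation in four (25%) is certain.
- Block of 8 (simulated): 47% correct, 14% certain.
- Block of 12 (simulated): 44% correct, 10% certain.
- List read directly: 100% for any block size.

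The last line is the exposure that on-site storage creates and that hiding the block size cannot reduce.

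**3. Are the blinded roles consistent?**

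| Statement | Section |
|---|---|
| Randomising study therapist does no outcome assessment | 5.7 |
| Study therapists only implement the randomisation | 5.7 |
| Study therapist, blind, does baseline and monthly assessments | 7 |
| Study therapists collect nutritional data | 5.2 |
| Assessors not blinded | 7 |
| Pathology technician blind | 7 |
| Research team analyses without allocation | 7 |

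The first two rows conflict with the next two unless there are two separate sets of therapists, and no section creates them. The third and fifth rows conflict whichever therapists are meant. The last two rows are consistent with everything else.

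**The case against.** The strongest reply is that the text does describe a concealment system: numbered closed envelopes, delayed release of the code, an independent investigator, and a therapist explicitly kept out of recruitment, with enrolment done by other staff. This stands. A reader might infer that allocation is not concealed and that recruiters can know every future assignment. The protocol does not say that recruiters may read the list. It says only where the list is kept and is silent on access.

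A reader might also infer that single-blind is untrue, or that only the laboratory technician could be blind. Neither follows. The term is never tied to a party, and section 7 describes both the technician and the analysts as working without the allocation.

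It could be argued too that collecting diet and sun records reveals the arm. The flow chart in section 5.1 lists these items by group. However, the table in section 5.2 schedules the dietary and sun-exposure examinations at every visit without restricting them to an arm, and the accompanying text does not restrict them either. Only the pill count is clearly specific to one arm, and it is assigned to no named role.

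Finally, study therapists are mentioned in the plural, so sections 5.7 and 7 might describe different people. That reading is possible, but the protocol never states the split, and it would not remove the contradiction within section 7.

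**Conclusion.** The protocol should be corrected before recruitment relies on it. Two things are established:

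- Concealment is claimed but not assured. The complete list is kept at both recruiting centres throughout with no access restriction, and none of the stated safeguards addresses that.
- The blinding description is contradictory. The therapist who handles allocation is excluded from assessment in section 5.7, the assessing therapist is blind in section 7, and section 7 then says assessors are not blinded. Single-blind is therefore undefined, and it is contradicted for the clinic-collected anthropometry, diet and sun-exposure data.

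The size of the first problem is conditional: 100% predictability for anyone who reads the list, against 44% to 52% for someone with only past allocations and the block size. It rests on access occurring, which the protocol neither permits nor prevents, and the comparison rests on assumed block sizes. The blinding contradiction does not reach the measurement of the primary outcome, HbA1c (section 2.1), because the laboratory is described as blind. A failure of concealment could reach it, through who enters which arm, and could not be repaired after randomisation. That is why the change is worth making although no breach is shown.

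**What to change.** 1. **Section 5.7.** Delete storage of the list at the centres and the transfer of the sequence to study therapists. State that the independent investigator already named there holds the only list, off site. That person either prepares sequentially numbered, opaque, sealed envelopes or releases each allocation once consent and eligibility have been logged.
2. **Synopsis and sections 3.1, 5.7 and 7.** Reconcile them by stating that participants and clinic assessors are not blinded and that the laboratory technician and the analysts are. Replace the bare term single-blind with that description.
3. **Section 7.** Remove the sentence on the blind study therapist. Keep it only if the assessing therapists are existing staff who neither hold the sequence nor open envelopes, and in that case say so and delete the later statement that assessors are not blinded.

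The cost is protocol wording and moving custody of one list to a role that already exists. Keeping the assessing therapists blind under item 3 could need more people. The protocol gives no staffing numbers, so this should not be assumed to be free.

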6.1. ADVERSE EVENT REPORTING*

Adverse event

Adverse events will be collected after the participant has provided consent and enrolled in the study. In the current trial, the dosage of vitamin D (500 IU) provided through supplement, dietary or sun exposure is considered to be safe and it is unlikely to cause adverse effects. However, if participants report any adverse effects, they will be provided with medical treatment if necessary and excluded from the trial.

In addition, there is the possibility that in the dietary intervention group, some participants may report food intolerance and allergy symptoms to seafood or dairy products. Research staff will record the incidence. Participants will be asked to attend a dietitian review for appropriate suggestions to minimize the risk of further food intolerances/allergies. If the adverse effects continue, participants will be excluded from the trial and provided with relevant test and medical treatment if necessary.

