The vitamin D supplement group will be given an oral vitamin D supplement to ingest, dosage set as 500 IU per day. The dietary intervention group will be asked to follow a 'vitamin D food resources' list to obtain 10-15 μ g/d of vitamin D from food. The sun exposure group will be required to expose about 15% of body surface (hands, face and arms) to natural sunlight anytime from 10am to 4pm for 3-4 minutes/d from December to January, or 8 minutes/d from July to August or 10— 11 min/d from February to June or September to November, to get approximately 12.5 μ g/d of vitamin D per day. No interventions will be given to the wait list control group.

The total study period of the trial is 9 months. A face-to-face adherence reminder and examination session will occur at baseline and on a monthly basis. A blood test of vitamin D level and DM biomarkers will be obtained at baseline, and at the 3rd month and 9th month session. Participants who report with any side effects or upset symptoms will be assessed by study therapists and excluded from the trial once being confirmed.

Statistical considerations

Sample size calculation: By setting the significance level α =0.05, the power 1- β = 0.8 based on Campbell & Machin (1993) formula: m=(Z α + Z2 β)2{ π 1(1- π 1)+ π 2(1- π 2)}/ δ 2, (Z α + Z2 β)2 = 7.849, δ = π 2- π 1=0.7-0.35= 0.35; m=28. Therefore for the current study, the sample size of each group is calculated as at least 28, hence it requires at least 112 participants in total. With the consideration of a dropout rate 10%-20%, it is planned to recruit 31-34 participants per group with 123-134 participants in total.

Analysis plan: Data are expressed as means ± SDs. Initially, the Kolmogorov–Smirnov goodness-of-fit test will be used to assess the normal distribution of variables. Secondly, two-factor repeated-measures analysis of variance (ANOVA) will be used with Bonferroni correction in the current trial with time stages and

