6.2. EARLY TERMINATION

The vitamin D dosage used in this study is considered to be of a safe level for daily intake and is currently recommended as the AI for vitamin D in Australia. It is unlikely to cause any side effects or symptoms by obtaining this dosage level through sun exposure, dietary change or supplementary intake. However, some participants may experience allergy or food intolerance risks by adding seafood or eggs into their daily meals even if cleared from allergy history at the initial screening. Participants with any severe allergic reaction or food intolerance will be excluded from current study, relevant medical treatment including allergy test would be arranged for participants if necessary.

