8. STATISTICAL CONSIDERATIONS*

By setting the significance level α =0.05, the power 1- β = 0.8 based on Campbell & Machin (1993) formula: m=(Z α + Z2 β)2{ π 1(1- π 1)+ π 2(1- π 2)}/ δ 2, (Z α + Z2 β)2 = 7.849, δ = π 2- π 1=0.7-0.35= 0.35; therefore m=28. Therefore the sample size for each group in the current study was calculated to be

at least 28, with at least 112 in total. With the consideration of a dropout rate 10%-20%, it is planned to recruit 123-134 participants in total hence 31-34 participants for each group.

Data are expressed as means ± SDs. Initially, the Kolmogorov–Smirnov goodness-of-fit test will be used to assess the normal distribution of the values. Secondly, two-factor repeated-measures analysis of variance (ANOVA) with a Bonferroni correction will be used in the current trial with time stages and interventions as factors. Tukey's post-hoc comparison will be applied to identify the differences between four intervention groups at 3 months and 9 months in the case of significant interaction finding in ANOVA. Thirdly, correlations between variables will be evaluated by using either a Pearson (r) (for data with normal distribution) or a Spearman (rs) (for data with no normal distribution) correlation. A p-value <0.05 is considered to be statistically significant. All statistical analyses will be computed using the Statistical Package for Social Science version 17 (SPSS, Chicago, IL, USA). Missing values are to be treated according to the last observation carried forward (LOCF) method and will be assessed via sensitivity analysis.

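### Participants with adverse effects leave the trial, not just the intervention, so their later HbA1c is lost and filled by LOCF

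*Protocol*

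**What the plan says.** The protocol deals with adverse effects in five places, and each ends in removal from the study.

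- **Synopsis, study procedures:** "Participants who report with any side effects or upset symptoms will be assessed by study therapists and excluded from the trial once being confirmed".
- **Section 5.2, adverse event assessment (diet-arm food reactions):** "If the adverse effects continue, participants will be excluded from the trial, allergy test and related medical treatment will be provided if necessary". Dietitian advice comes first.
- **Section 5.3:** the general rule is "if participants report with any adverse effects, they will be provided with medical treatment if necessary and excluded from the trial". A separate paragraph on diet-arm food reactions provides a dietitian review first and exclusion if the reaction persists.
- **Section 6.1:** the general rule is "if participants report any adverse effects, they will be provided with medical treatment if necessary and excluded from the trial". For diet-arm reactions, after dietitian review, "If the adverse effects continue, participants will be excluded from the trial and provided with relevant test and medical treatment if necessary".
- **Section 6.2:** "Participants with any severe allergic reaction or food intolerance will be excluded from current study".

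HbA1c is the measure named in the primary objective (section 2.1). Blood is taken only at baseline, month 3 and month 9 (Synopsis; section 5.2). Section 8 states: "Missing values are to be treated according to the last observation carried forward (LOCF) method and will be assessed via sensitivity analysis".

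**The concern.** Stopping an intervention that may be causing harm is right. Removing the person from the trial is a separate step, and it takes away outcome data after randomisation for a reason connected with the allocation.

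The loss is unlikely to be balanced. The wait-list arm receives nothing that could cause a reaction. Participants know their arm (section 7: "neither participants nor assessors will be blinded to the intervention"). The only reactions the protocol specifically foresees are food intolerance and allergy in the diet arm. Adverse events are assessed at study visits, so removal also ends scheduled safety follow-up for the people who reported harm.

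The trigger is also unclear. If the general rule is a report of any effect, one mild and passing complaint ends participation. If it is confirmation by a study therapist, it may not. Staff who follow different sections could treat the same event differently.

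**Working it through.** **1. The rules side by side**

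| Place | Trigger | Removed from |
|---|---|---|
| Synopsis | any side effect, once confirmed by a study therapist | the trial |
| 5.2 (diet) | food reaction that persists | the trial |
| 5.3, general | any reported adverse effect | the trial |
| 5.3, diet | food reaction that persists after dietitian review | the trial |
| 6.1, general | any reported adverse effect | the trial |
| 6.1, diet | food reaction that persists after dietitian review | the trial |
| 6.2 | severe allergic reaction or food intolerance | the study |

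The diet rules can be read as escalation: persistent reactions in 5.2, 5.3 and 6.1, severe ones in 6.2. The general rule remains inconsistent, because 5.3 and 6.1 act on a report and the Synopsis acts on a confirmed event. No row limits removal to the intervention, and none keeps the later blood tests. What is offered is medical treatment and allergy testing where needed.

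**2. Arm size, reproduced from section 3.3**

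- Per group: 7.849 × [0.35 × 0.65 + 0.70 × 0.30] / 0.35² = 28.03, stated as 28, so 112 in total.
- With dropout: 112 × 1.10 = 123.2 and 112 × 1.20 = 134.4, stated as 123-134, or 31-34 per group.
- One exclusion is therefore 1/34 = 2.9% to 1/31 = 3.2% of an arm's 9-month data.

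**3. What LOCF does to the arm mean**

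Let *f* be the share of an arm excluded. Let *g* be the carried-forward HbA1c minus the value that would have been measured at month 9. The carried value is baseline if exclusion comes before month 3, and the month-3 value if it comes later. Then

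bias in the arm's 9-month mean = *f* × *g*.

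The protocol gives neither quantity, so both are assumed:

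| *f* (assumed) | *g* = 0.1 | *g* = 0.5 |
|---|---|---|
| 3% | 0.003 | 0.015 |
| 10% | 0.01 | 0.05 |
| 20% | 0.02 | 0.10 |

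Units are HbA1c points. With no exclusions in control, this is also the bias in the between-arm difference. Its sign follows the sign of *g*.

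**4. Exclusion before month 3**

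Only baseline exists, so LOCF sets the person's change to zero at both later times. If those excluded would otherwise have changed like the rest of the arm, the arm's estimated change is (1 − *f*) of its true value: 95%, 90%, 85% and 80% for *f* = 5%, 10%, 15% and 20%. People who stop the intervention may change less than the rest, and the shrinkage would then be smaller.

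**5. If those excluded are left out of the analysis instead**

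On the protocol's own 35% versus 70% planning rates, 34 per arm less 20% dropout leaves 27.2, with power of about 75% (pooled normal approximation). A further assumed 5-15% excluded in both arms leaves 25.8 to 23.1, with power of about 73% to 67%.

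**The case against.** Four points can be made for the protocol.

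- **Non-collection is an inference.** No section says that blood tests stop, and section 8 does not mention excluded participants when it names LOCF. That is so. But exclusion from the trial with no follow-up described has no other natural reading, and LOCF is the only rule given for missing values. If those excluded were dropped from the analysis instead, the data would still be lost.
- **The triggers largely fit together.** Diet rules stand beside a general rule, persistent and severe reactions can be escalation steps, and the short wording in 5.3 and 6.1 may be shorthand for the Synopsis procedure. The escalation reading is fair. The difference between a reported and a confirmed effect remains, but it is a matter of wording and does not carry this point.
- **The effect may be negligible.** Every share and gap above is assumed, and the protocol expects such effects to be unlikely. A 20% share would by itself equal the top of the 10-20% dropout allowance. The absence of exclusions in control is also an assumption, since adverse events are assessed in all arms. This stands, and it limits how strongly the point can be put.
- **A sensitivity analysis is planned.** It can show how far the result depends on LOCF. It cannot replace values that were never measured, and nor can a statistical analysis plan, because this is a rule about conduct and data collection.

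**Conclusion.** The concern holds and should be fixed. Followed as written, the protocol loses primary-outcome data after randomisation for a reason tied to the allocated arm, and it ends scheduled safety follow-up for the people affected. Under the assumed 3-20% excluded and gaps of 0.1-0.5 points, the bias runs from 0.003 to 0.10 HbA1c points. The low end, about one person per arm, is negligible and is the likelier case if adverse effects are as rare as the protocol expects. The actual size cannot be derived from the document. The case for acting rests on the loss being irreversible and the remedy cheap.

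**What to change.** In the Synopsis and sections 5.2, 5.3, 6.1 and 6.2:

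- Replace removal from the trial with three steps: stop the allocated intervention, continue adverse event follow-up, and take the scheduled month-3 and month-9 blood tests unless the participant withdraws consent.
- State one trigger for stopping, chosen by the investigators, and use it in every section.
- Analyse the measured values in the arm as randomised, in place of carried-forward ones.

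Medical treatment and allergy testing stay as they are, so participants lose no protection. The cost is a short amendment and at most two already planned blood tests for each of a few participants.
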